6.2.3 Assessment of cellular immune responses

Approximately 30 mL of whole blood will be obtained from subjects prior to vaccination and at time points after vaccination for assessment of B- and T-cell responses to AMA-1. These samples will be assayed for:

6.2.3.1 B Cell phenotype by flow cytometry:

AMA-1 specific activated B cells will be detected by staining with CD19, CD20, CD27, CD38, and Alexafluor-conjugated AMA-1. Results will be compared to those using fluorescently labeled BSA. Precise cell counts will be performed by Coulter counting to allow extrapolation of the FACS percentages to lymphocyte populations in peripheral blood of subjects.

6.2.3.2 Malaria-specific T cell effector cytokines:

Malaria-specific T cell responses will be evaluated by three single-color cytokine (IL2, IL4, IFN- γ) ELISPOT assays of PBL. In addition, FluoriSPOT assays using three-fluorescent dyes simultaneously will be performed in parallel in order to compare this assay, which has greater potential for automation and a larger dynamic range, with the ELISPOT results. In these assays AMA1-3D7 and AMA1-FVO will be used as antigens. If the frequency of T cell effectors is too high, the spot rate in diluted samples will be assessed, capturing B cell and naturally-adherent APC on the ELISPOT filters with anti-CD19 mAb to avoid dilutional effects in antigen presentation.

Finally, production of multiple cytokines and chemokines by antigen-specific T cells will also be assessed by in vitro stimulation of PBL with AMA1-FVO and AMA1-3D7 proteins using a quantitative multiplex bead ELISA (Luminex) system.

6.3 USE, STORAGE, AND TRACKING OF SPECIMENS AND DATA

Samples and data collected under this protocol will be used to study malaria and related diseases, and possible adverse reactions to vaccination. No genetic testing will be performed. Access to research samples will be limited using either a locked room or a locked freezer. Samples and data will be stored using codes assigned by the investigators or their designees. Data will be kept in password-protected computers. Only investigators or their designees will have access to the samples and data.

Samples will be stored at the MVDB in Rockville, MD or at MVDB's designated repository, Thermo Scientific, Rockville, MD. Samples will be tracked using a software database, e.g. Freezerworks. Any loss or unanticipated destruction of samples (for example, due to freezer malfunction) or data (for example, misplacing a printout of data with identifiers,) will be reported to the IRBs. Such a loss will be reported to the NIAID IRB as a protocol violation under the following classification: The violation compromises the scientific integrity of the data collected for the study.

6.4 RETENTION OF SPECIMENS FOR FUTURE USE

All specimens collected as part of this trial may, with the subject's permission, be stored for future research. Whether or not a volunteer agrees to storage of specimens will not affect his/her ability to participate in this trial. These samples may be used to learn more about malaria infection and other diseases. These samples will not be sold or used to make

commercial products. Samples will only be stored with the volunteer's permission. The volunteer may withdraw permission for future use of specimens at any time. If a volunteer withdraws his or her permission for future use of specimens, those specimens will be destroyed. All samples stored will be labeled with the volunteer's study identification (ID) number, which cannot identify the study subject but is linkable to other research databases (e.g., from questionnaires, clinical assessments, logbooks, etc.) generated by the main study. The database will contain only the study volunteer's ID number. A master log linking the study volunteer ID number to the name of the volunteer will be maintained in a password protected database system with access limited to authorized research team members.

At the completion of the protocol (termination), samples and data will either be destroyed, or after IRB approval, transferred to another existing protocol or a repository. In the future, other investigators (both at NIH and outside) may wish to study these samples and/or data. In that case, IRB approval must be sought prior to any sharing of samples. Any clinical information shared about the sample with or without patient identifiers would similarly require prior IRB approval. The research use of stored, unlinked or unidentified samples (for example, as a standard for immunological analyses), may be exempt from the need for prospective IRB review and approval. Exemption requests will be submitted in writing to the NIH Office of Human Subjects Research, which is authorized to determine whether a research activity is exempt.

7 ASSESSMENT OF THE SAFETY OF VACCINATION

Safety will be assessed by frequency and incidence of AEs and SAEs in each treatment group.

7.1 SAFETY PARAMETERS

Safety parameters will include diary cards which record symptoms from days 0-6 following each vaccine, vital signs at each study visit, recording of daily oral temperature for 6 days following vaccination, laboratory studies, and unsolicited adverse events.

7.2 METHODS AND TIMING OF SAFETY ASSESSMENTS

Subjects will be asked to keep daily symptom diaries recording oral temperature once daily, as well as pain, tenderness, redness, and induration at the injection site for six days

following each immunization. The size of any injection site reaction will be measured utilizing a standardized clear plastic measurement device and recorded in the volunteer symptom diary. See Appendix 17.4.

Using standard techniques, the clinical laboratory, will perform the following tests:

1. Complete blood count plus white blood cell differential (parameters to be assessed for safety: WBC, Platelet count, Hemoglobin)
2. Serum creatinine
3. Aspartate aminotransferase (AST)
4. Urinalysis (in the event of an abnormal urine dipstick test)
5. Rheumatoid factor - laboratory cut-off for negative results = "negative"
6. Anti-dsDNA (ELISA) – laboratory cut-off for negative result < 1:4
7. ANA – laboratory cut-off for negative result \leq 1:80
8. C3
9. C4
10. CH50

Urine β -hCG testing will be performed at the clinical trial site, using an FDA-approved urine pregnancy test kit. Urine dipstick testing will be performed at the clinical trial site using an FDA-approved product.

7.3 ADVERSE EVENTS, REACTOGENICITY, SERIOUS ADVERSE EVENTS

The Investigator is responsible for reporting all AEs that are observed or reported during the study, regardless of their relationship to study product. Initial vaccine reactions will be assessed at 30 minutes after vaccination following each vaccine dose. Subjects will be asked to record both solicited vaccine reactions (from 0 [not present] to 3+ [severe]) and any unsolicited AEs on a diary card for 6 days following both vaccinations.

Solicited systemic AEs will include the following: Feverishness/chills, malaise body aches (exclusive of the injection site), rash, loss of appetite, and headache.

Solicited injection site AE will include the following: Pain or tenderness, redness, and swelling.

7.3.1 Definition of Adverse Event

Adverse Event: ICH E6 Good Clinical Practice Guidelines defines an Adverse Event (AE) as any untoward medical occurrence in a patient or clinical investigation subject administered a pharmaceutical product regardless of its causal relationship to the study treatment. An AE can therefore be any unfavorable and unintended sign (including an abnormal laboratory finding), symptom, or disease temporally associated with the use of medicinal (investigational) product. The occurrence of an adverse event may come to the attention of study personnel during study visits and interviews or by a vaccine recipient presenting for medical care.

All adverse events must be graded for intensity and relationship to study product

Changes in the severity of an AE should be documented to allow an assessment of the duration of the event at each level of intensity to be performed. Adverse events characterized as intermittent require documentation of onset and duration of each episode.

Relationship to study products/vaccines: The investigator's assessment of an AE's relationship to study drug/vaccine is part of the documentation process, but it is not a factor in determining what is or is not reported in the study. If there is any doubt as to whether a clinical observation is an AE, the event should be reported. All adverse events must have their possible relationship to study vaccine assessed using the following terms: associated or not associated. In a clinical trial the study product must always be suspect. To help assess, the following guidelines are used.

- Associated – There is a known temporal relationship with study product administration and definite no other compelling etiology. Associated adverse events include those AEs judged to be definitely, probably, possibly, or unlikely related to vaccination.
- Not Associated -the AE is temporally independent of study product administration; and a compelling alternative etiology exists

Relationship of AEs to study product will be coded on a dual scale so that assignment of associated/not associated or definitely/probably/possibly/unlikely/not will both be captured and can be reported either way.

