3.3 MEASURES TO AVOID BIAS

Subjects within each cohort will be blinded as to study assignment.

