5.3 RANDOMIZATION

The eligible subjects assigned to each of the three cohorts will be asked to come to the clinic for their scheduled day 0 visit. After a history and physical exam is performed to ensure

that they are eligible for participation in the study, blood will be collected for the studies outlined in Section 5.21. Study participants will be assigned a unique study number.

Randomization to either the AMA1-C1/Alhydrogel[®] + CPG 7909 vaccine or 80 µg AMA1-C1/Alhydrogel[®] vaccine will be done online using the enrollment module of the Internet Data Entry System (IDES). The randomization codes will be included in the enrollment module for the trial. Each subject enrolled into the trial is assigned a treatment code after demographic and eligibility data have been entered into the system. The site will be provided with a code list to be kept in a secure place.

5.4 IMMUNIZATION PROCEDURE:

Subjects will receive three immunizations, on Days 0, 28, and 56. 0.50 mL of AMA1-C1/Alhydrogel[®] or 0.55 mL of AMA1-C1/Alhydrogel[®] + CPG 7909 will be delivered by IM in the deltoid muscle with a 22-gauge needle of appropriate length after preparation of the site with alcohol. Successive vaccinations will be given in alternating arms.

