9.2 Endpoints

9.2.1 Safety

The primary safety endpoint is the frequency of vaccine-associated AEs, as classified by severity through active and passive surveillance. Separate assessments of systemic and local reactions will be performed.

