9.3 Analysis Plan

Primary Objective 1: To assess the safety, reactogenicity and immunogenicity of the AMA1-C1/Alhydrogel[®] + CPG 7909 vaccine at each dose

- a. Summarize the frequency of immediate, systemic, and local AEs.
- b. Line listing of individual clinical and laboratory AEs as classified by immediate (within the first 30 minutes), systemic, and local will be displayed in tabular format and stratified by dose cohort.
- c. AEs will be summarized by severity and relationship to vaccine by individuals and dose cohort.

Secondary Objective 1: To demonstrate that the addition of CPG 7909 improves the immune responses to AMA1-FVO and AMA1-3D7, as compared to AMA1-C1/Alhydrogel[®] at day 70.

a. Mann-Whitney tests will be used to compare the antibody concentrations between groups. Specifically, the subjects receiving 80 µg AMA1-C1/Alhydrogel[®] + CPG 7909 will be compared to those receiving only 80 µg AMA1-C1/Alhydrogel[®].

Secondary Objective 2: To determine whether increasing dose increases the serum antibody levels to AMA1-FVO and AMA1-3D7 at day 70 in the AMA1-C1/Alhydrogel[®] + CPG 7909 groups.

a. A Mann-Whitney test will be performed on the two dose levels.

Secondary Objective 3: To assess and compare the duration of antibody responses to AMA1-FVO and AMA1-3D7.

- a. Describe immunogenicity responses by dose, over time from ELISA data.
- b. Individual responses will be described over time and stratified by dose cohort.
- c. Analysis will be performed using longitudinal models.

Secondary Objective 4: To perform exploratory studies of B and T cell populations before and after vaccination

Other analyses:

1. To measure the inhibition of parasite growth as measured by the in vitro GIA to both FVO and 3D7 parasite clones.

a. Growth inhibition, expressed as a percent of inhibition comparing test sera to pre-immune sera, will be displayed graphically.

2. To determine the relationship between anti-AMA1 antibody concentration and degree of in vitro growth inhibition of *P. falciparum* in a GIA.

a. Rank correlation between ELISA values and growth inhibition will be assessed by the Spearman Rank correlation test.

b. Growth inhibition values will be plotted graphically as a function of ELISA units of antibody of each serum and stratified by dose.

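### The primary safety endpoint uses conflicting causality categories, leaves the blinding of those who attribute events unstated, and is tabulated by a cohort term that blurs the CPG 7909 comparison

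*Protocol*

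**What the plan says.** **Endpoint.** Protocol 9.2.1: "The primary safety endpoint is the frequency of vaccine-associated AEs, as classified by severity through active and passive surveillance".

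**Definitions.** Protocol 7.3.1 gives this guideline for *associated*: "There is a known temporal relationship with study product administration and definite no other compelling etiology". The next sentence reads: "Associated adverse events include those AEs judged to be definitely, probably, possibly, or unlikely related to vaccination". For *not associated* the guideline is "the AE is temporally independent of study product administration; and a compelling alternative etiology exists". The same section makes the assessment the investigator's. It says that the two-way code and the five-level code "definitely/probably/possibly/unlikely/not will both be captured and can be reported either way".

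**Blinding.** The whole of 3.3 is one sentence: "Subjects within each cohort will be blinded as to study assignment". Section 3.2 likewise speaks only of subjects. Section 3.8 has the study pharmacist keep the codes, with a sealed backup held by the on-site medical monitor. Section 5.3 adds: "The site will be provided with a code list to be kept in a secure place". No holder is named there. Section 5.4 gives injected volumes of 0.50 mL without CPG 7909 and 0.55 mL with it.

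**Tabulation.** Protocol 9.3, under the primary objective: "AEs will be summarized by severity and relationship to vaccine by individuals and dose cohort". The line listing is stratified the same way. The opening of Section 7 instead assesses AEs and SAEs by treatment group, and 3.1.1 also refers to groups. The table in 3.2 gives the allocation: Cohort 1 has 15 A and 5 C, Cohort 2 has 15 B and 5 C, and Cohort 3 has 15 B and 20 C.

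**The concern.** The endpoint is a filtered count: an event enters only if someone judges it associated. Three things weaken that count.

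- **The filter is not well defined.** Two investigators could follow the text and code the same event in opposite ways. This happens at the site under the protocol, so later analysis cannot fully repair it. Events judged *unlikely* also add background to a measure meant to describe the CPG 7909 formulation.
- **The person applying the filter is not stated to be blinded.** The risks of CPG 7909 are set out in advance in 1.4. Knowledge of the arm could therefore influence attribution, especially for unsolicited and laboratory events.
- **The table layout is in doubt.** The synopsis describes the three enrolment stages as dose-escalation cohorts, so *dose cohort* is naturally read as Cohorts 1 to 3. Reading it as dose level does not separate the arms either, because Groups B and C both receive 80 µg. On either reading the concurrent controls would be mixed with CPG recipients.

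At stake is how clearly the primary safety result shows what CPG 7909 adds, in a trial that randomises 30 controls.

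**Working it through.** **The plan's own safety figure.** Section 9.4 gives a probability of about 0.8 of seeing at least one serious or severe AE in 15 subjects when the true rate is 0.1. The check is 1 − 0.9^15 = 0.794, which reproduces it. The figure concerns one group and says nothing about a difference between arms.

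**Definitions.** Cross the two conditions in 7.3.1, temporal relationship (yes or no) and compelling other cause (yes or no):

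- related in time, no other cause: *associated*;
- not related in time, other cause: *not associated*;
- related in time, other cause: meets neither guideline;
- not related in time, no other cause: meets neither guideline.

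Two of the four combinations have no home. The sentence that places *unlikely* under *associated* could sweep in the third, but only by overriding the condition stated just before it.

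**Dilution by *unlikely* events (assumed rates; the protocol gives none).** Let related AEs occur in 40% with CPG and 15% without: difference 25 points, ratio 0.40/0.15 = 2.7. Let a further share b of subjects in both arms have an independent, unrelated event coded *unlikely*. The counted rates become 1 − 0.60(1 − b) and 1 − 0.85(1 − b):

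- b = 0.2: 52% v 32%, difference 20 points, ratio 1.63;
- b = 0.4: 64% v 49%, difference 15 points, ratio 1.31;
- b = 0.6: 76% v 66%, difference 10 points, ratio 1.15.

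**Tables by enrolment cohort (assumed 60% in A and B, 20% in C).**

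- Cohorts 1 and 2: (15 × 0.6 + 5 × 0.2)/20 = 10/20 = 50%.
- Cohort 3: (15 × 0.6 + 20 × 0.2)/35 = 13/35 = 37%.

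No row shows the 40-point difference. Cohort 3 looks safer only because 15/35 = 43% of it receives CPG, against 15/20 = 75% in the other two.

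**Precision of B minus C.** B is randomised against C only in Cohorts 2 and 3: 15 + 15 = 30 B and 5 + 20 = 25 C. At the same assumed rates the half-width of the 95% CI, ignoring cohort, is 1.96 × √(0.24/30 + 0.16/25) = 1.96 × 0.12 = 23.5 points. Stratifying costs little. The variances are 0.24/15 + 0.16/5 = 0.048 in Cohort 2 and 0.24/15 + 0.16/20 = 0.024 in Cohort 3. The inverse-variance combination is 1/(1/0.048 + 1/0.024) = 0.016, so the half-width is 1.96 × √0.016 = 24.8 points.

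**The case against.** A reader might infer that the endpoint cannot show what CPG 7909 adds, that AEs will be analysed by cohort instead of by arm, and that assessors know the assignment. The protocol supports none of these.

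- Section 7 and 3.1.1 refer to groups, and *dose cohort* is never defined. The fault is a conflict with 9.3, not a settled choice against analysis by arm. The phrase *by dose* in 9.3 describes ELISA responses and growth-inhibition plots, not AE tables.
- The five-level code is kept and reportable, so a count without *unlikely* can be recovered. Section 9.3 also summarises AEs without a relationship filter. Under the dilution assumed above, a difference of 10 to 20 points remains.
- Staff blinding is unstated, not denied. Pharmacist-held codes and a sealed backup suggest restricted access, and solicited reactions are recorded by blinded subjects.
- The broad definition is deliberately cautious and matches the halting rules in 7.7.
- Section 9.1 calls the study exploratory, the primary objective names no comparison, and table layout is commonly left to an analysis plan.

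All of this limits the point. It does not remove the contradiction in 7.3.1, which acts when events are coded at the site. Diaries kept by blinded subjects do not protect the investigator's attribution of unsolicited or laboratory events. Two sections of one protocol still disagree on how AEs are grouped. The B minus C estimate is a recommendation, not a charge of omission; it fits the aim in 9.1 of presenting estimates with 95% intervals.

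**Conclusion.** The concern holds as three defects of wording that bear on the primary safety result: causality categories that are neither consistent nor exhaustive, unstated blinding of the people who apply them, and a tabulation term that conflicts with Section 7. Together they dilute and obscure the CPG 7909 contrast but leave it recoverable from the data collected.

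The sizes rest on assumed rates. Cohort tables would show 50%, 50% and 37% in place of 60% v 20%. Counting *unlikely* events would cut a 25-point difference to between 20 and 10 points if 20% to 60% of subjects have such an event, and that range has no source in the protocol. The cohort figures also assume that *dose cohort* means the enrolment cohort with its arms merged. No size can be given for attribution bias. The changes are worth making before the first AE is coded.

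**What to change.** 1. **9.3.** Replace *dose cohort* with Groups A, B and C, in line with Section 7. Report the B minus C difference in AE rates with a 95% CI from Cohorts 2 and 3, stratified by cohort because allocation differs (3:1 and 3:4), for associated AEs and for all AEs.
2. **3.3, 3.8 and 5.3.** State that the clinicians who grade and attribute AEs are blinded, that the pharmacist prepares masked syringes, and that the pharmacist holds the site code list.
3. **7.3.1.** Rewrite both definitions so that every event falls in exactly one category. Moving *unlikely* alone is not enough, because the *not associated* text would still exclude an event close to a dose that has another cause. Report the endpoint with and without *unlikely*, using the five-level code already captured.
4. **Consistency.** Sections 4.4.2, 7.4.1 and 7.7 use *associated* for withdrawal, reporting and halting. They must be reconciled with the revised term; this point does not propose what those clinical rules should be.

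The cost is protocol wording, revised table shells, slightly more analysis and a masked syringe.

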7.3.2 Reactogenicity Grading Scale

The grading scales for solicited clinical reactions, and for laboratory abnormalities, are given in appendix 17.2 and 17.3. Unsolicited clinical reactions will be graded according to appendix 17.5.

7.3.3 Definition of a Serious Adverse Event

A Serious Adverse Event is defined as an AE meeting one of the following conditions:

- Death during the period of protocol defined surveillance
- Life Threatening (defined as a subject at immediate risk of death at the time of the event)
 - Requires inpatient hospitalization or prolongation of existing hospitalization during the period of protocol defined surveillance
 - Results in congenital anomaly or birth defect
 - Results in a persistent or significant disability/incapacity.
 - Any other important medical event that may not result in death, be life threatening, or require hospitalization, may be considered a serious adverse experience when, based upon appropriate medical judgment, the event may jeopardize the subject and may require medical or surgical intervention to prevent one of the outcomes listed above. Examples of such medical events include allergic bronchospasm requiring intensive treatment in an emergency room or at home, blood dyscrasias or convulsions that do not result in inpatient hospitalization, or the development of drug dependency or drug abuse.

7.4 REPORTING PROCEDURES

Adverse Events including local and systemic reactions not meeting the criteria for “serious adverse events” will be captured on the appropriate case report form. Information to be collected includes event description, date of onset, investigator assessment of severity, relationship to study product, date of resolution of the event, seriousness, and outcome. All adverse events occurring while on study will be documented appropriately regardless of relationship. All AEs will be followed to adequate resolution.

Any medical condition that is present at the time that the patient is screened will be considered as baseline and not reported as an AE. If the severity of any preexisting medical condition increases during the study period, then it will be recorded as an AE.

